5.3 Study procedures

Couples matching the inclusion criteria will be asked to participate in the trial. If after diagnostic work up the diagnosis infertility for the couple remains, both are asked for informed consent. After signing informed consent, the male patient will be randomised and allocated to Impryl® or placebo (double blinded).

Medication

Patients can directly start using the food supplement or placebo. Impryl® or placebo will be taken for a total duration of 6 months and will be directly stopped after having a positive pregnancy test.

Baseline characteristics

Patients are asked to report on these characteristics by a short questionnaire. Patients will receive an automatic email invitation directly after randomisation and are asked to provide this information online in the Castor database system

Lifestyle and outcome characteristics

Patients will be asked once every month to report on occurrence of pregnancy (with date of positive test), changes in weight and diet, changes in habit of smoking and drug or alcohol use, occurrence of fever and change in activities increasing scrotal temperature (hot baths, sauna, race cycling). Furthermore patients are instructed about taking note of the total amount of consumed study medication (used boxes and tablets). There is a question about the occurrence of adverse events. Patients will receive an automatic email and are asked to provide this information online in the Castor database system. When a pregnancy has been reached during the 6 months use of study medication the monthly questionnaires will be stopped, because there is no more necessity to record on lifestyle changes and treatment compliance.

Semen analysis

Semen analysis will be performed two times: once during diagnostic work-up (standard care, analysis according to WHO criteria(28) and once more after approximately 3 months of using study medication (ie. after three months of IUI treatment or IVF/ICSI). At several sites, a pre-wash TMSC is standard care when performing an insemination (IUI group) and will be performed on the semen produced for IVF/ICSI as part of routine measurement before procedure. Because semen analysis performed at the time of treatment cannot be fully performed according to the WHO criteria, we will categorize the TMSC quality according to the allocated treatment category. This means, that the TMSC (evaluated at the start of treatment and after 3 months) will be analyzed according to changes in allocated treatment category based on the NVOG guideline(29). The criteria for treatment are given in the table below. A change in treatment category means an improvement in sperm quality that would allow a lower treatment category (e.g, from ICSI to IVF)

| TMSC outcome ($\times 10^6$) | WHO Diagnostic category | NVOG Treatment category |
|--------------------------------|-------------------------|---|
| > 10 | Normospermia | EM |
| 3 -10 | Mild OAT | IUI |
| 1-3 | OAT | IVF/ICSI (if after wash VCM is <0,5) |
| <1 | Extreme OAT/Azoospermia | ICSI |

OAT = oligo-astheno-teratozoospermia.

* Or IVF depending on the prediction model of Hunault and other clinical characteristics

We decided not to perform a semen analysis in the EM group due to the fact that they already have normal semen parameters at intake and the burden of an extra visit is high.

Fertilization and embryo-utilization rate

In IVF/ICSI patients fertilization rate and embryo-utilization rate are standard reported by every IVF-laboratory. Fertilization rate is the percentage of oocytes with ≥ 2 PN after insemination (IVF) or injection (ICSI). The embryo-utilization rate (EUR) is defined as the number of high quality embryos obtained, embryo's used at transfer plus the number of embryos frozen, divided by the number of zygotes obtained in a cycle. Due to the differences in embryo evaluation and embryo selection criteria for cryopreservation, we decided to measure the relative increase in fertilization and utilization rate observed for each clinic.

Transvaginal ultrasonography

If there is a clinical pregnancy in fertility patients, a routine (standard care) ultrasound will be performed in the first trimester between 5 to 9 weeks to determine the viability. Also routine (standard care) is an ultrasound around 10-12 weeks to estimate the due date. To limit the amount of extra site visits to zero, we decided that this 'due date' ultrasound at 10-12 weeks of pregnancy is enough for determining the primary outcome. The ultrasound can be made in the midwife practice. Information about the outcome of this ultrasound is reported in the 15-months questionnaire.

Questionnaire pregnancy/treatment outcome

To allow follow-up for treatment and pregnancy outcome, all couples will receive an automatic email with invitation for a short questionnaire 15 months after inclusion. They will receive questions about fertility treatment and pregnancy outcome (ability to achieve a pregnancy, occurrence of miscarriage or childbirth, date of delivery, gestational age, mode of delivery, complications of delivery, birth weight and sex of neonate). An email will be sent if the questionnaire is not returned after one month. If there is no reaction to the reminder email, either the patient or his general practitioner will be contacted by telephone to answer follow-up questions.

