Nature and extent of the burden and risks associated with participation, benefit and group relatedness: Couples with infertility will receive standard fertility treatment, i.e. EM or ART. The risks and burden of participating in the trial are small. After a complete diagnostic work-up for infertility, the males will be randomised for use of either Impryl® or placebo. Impryl® is a food supplement already free available throughout Europe, online in the

Netherlands. Males need to take study medication (one tablet each day) for a maximum of 6 months in total. For this study, we want to measure improvement of semen parameters after at least 3 months use of study medication. Performing a pre-wash TMS is standard procedure at most sites when semen is used for IUI or IVF/ICSI. However, in couples with EM performing a TMS after 3 months is not standard care. We decided not to perform a semen analysis in the EM group due to the fact that improvement in fertility treatment from expectative management is not possible. Participants are required to collect study medication directly at their local hospital or at Radboudumc. At the start of taking study medication the couple is asked to fill in a questionnaire about their baseline characteristics. To assess lifestyle changes during intervention and amount of used study medication, every male will be asked each month (6 times in total) to fill in an online questionnaire, these monthly questionnaires stop when a pregnancy has been reached. Every couple will receive a final questionnaire, 15 months after inclusion, about the outcome of fertility treatment and occurrence of pregnancy. If a woman is pregnant, standard care is an ultrasound around 10-12 weeks to estimate the due date. To limit the amount of extra site visits to zero, we decided that this 'due date' ultrasound at 10-12 weeks of pregnancy is enough for determining the primary outcome. The ultrasound can be made in the midwife practice. Information about the outcome of this ultrasound is reported in the 15-months questionnaire. In conclusion, the burden and risks associated with participation in this trial can be considered negligible.

INTRODUCTION AND RATIONALE

[figure not shown]

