1.2 Inclusion criteria

In order to be eligible to participate in this study, a subject must meet all of the following criteria:

- Either: couples with failure to conceive for at least 12 months and starting with EM **or** couples starting with 1st/ 2nd/3rd cycle of IUI (with/without ovarian stimulation) **or** 1st/ 2nd/3rd cycle of IVF/ICSI
- Male with age 18-50 years
- Female partner with age 18-43 years
- Willing and able to give informed consent

Exclusion criteria

A potential subject who meets any of the following criteria will be excluded from participation in this study:

- Planned or performed diagnostic testicular biopsy (TESE) or percutaneous epididymal sperm aspiration (PESA)
- Use of donor-, cryopreserved- or electro-ejaculated semen
- Ovulation induction (OI) without IUI
- IVF for an absolute tubal factor
- Embryo-transfers after cryopreservation
- Embryo-transfer after pre-implantation genetic diagnosis
- Known endocrine abnormalities related to infertility, or use of fertility enhancing drugs
- Known genetic abnormalities related to infertility
- Known urological abnormality such as a varicocele or bilateral cryptorchism
- Use of other vitamin supplements

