2.2 Use of co-intervention

All couples will receive our standard care for infertility according to the guidelines of the Dutch Society of Obstetrics and Gynaecology. After diagnostic work up couples will either start with EM (6 months), IUI, IVF or ICSI. Participants will take study supplement for a maximum of 6 months, even if the fertility intervention (6 x IUI or 1 x IVF/ICSI cycles) is not completed. Co-treatment with other vitamins or supplements is prohibited. If vitamins or supplements are already used by men, a wash-out period of 3 months is recommended. Patients using other supplements will be excluded or reported as protocol violation. If after randomization it appears that a patient still uses other supplements (reported in the online questionnaire), they will be telephonically contacted and asked to stop use of other supplements. After this stop, there is a wash-out period of 72 days (duration of spermatogenesis). If no pregnancy occurs within this wash-out period the patient and data can still be included.

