5.1.3 Other study parameters

Baseline parameters are age, length, weight, ethnicity, alcohol/drugs/nicotine use, use of vitamins/steroids or other supplements, diet specifics (normal, vegetarian, vegan, gluten-free, dairy free, other), medication use, activities that cause increased scrotal temperature such as often visiting a sauna, taking a hot bath or race cycling, general health, operations or trauma in genital area, exposure to toxins in environment, conception of previous children, duration of infertility and type of diagnosis of infertility. Furthermore the age and parity of the female partner has to be documented, as well as the occurrence of endometriosis or anovulation.

Furthermore, when IVF/ICSI is performed, the amount of embryos transferred will be reported, either a single-embryo transfer (SET) or double-embryo transfer (DET).

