5.2 Randomisation, blinding and treatment allocation

RANDOMISATION AND TREATMENT ALLOCATION: All couples visiting a fertility specialist for the first time or for evaluation of fertility treatment will be informed on this study. Prior to or at their actual appointment they will receive the patient information (PIF). Randomisation will be performed, after signed informed consent has been obtained, using a web-based application (Castor). We will use permuted block-design, stratified for fertility treatment (1st) and recruiting centre (2nd). Block sizes are flexible. Participants will be randomised in a 1:1 ratio to study medication (Impryl®) or placebo. Assignment to medication, using the randomisation list, will either performed at the local centre or at Radboudumc by an independent person. This person is neither participating in clinical treatment nor processing the study data. Randomisation outcome is either A (Impryl®) or B (placebo).

CODING: coding starts immediately after informed consent has been obtained. In Castor each patient will receive a combination of one letter and 3 numbers. The code will be assigned as followed: Radboudumc (A), Slingeland (B), Canisius-Wilhelmina (C), Jeroen Bosch (D), Elisabeth-TweeSteden (E), Maasziekenhuis Pantein (F), Bernhoven (G), Maxima Medisch Centrum (H), Maastricht UMC+ (I), Gelre ziekenhuizen (J), Nij Geertgen (K) Rijnstate (L), Medisch Centrum Kinderwens (M), Nij Barrahûs (N),Fertiliteitscentrum Voorburg (O), Catharina Ziekenhuis Eindhoven (P) and Bravis Ziekenhuis (Q). For example, the first patient included in Radboudumc will receive the code A001. The code will not provide any information about the received intervention (Impryl® or placebo). The list of codes corresponding with patient information and received medication will be saved in an

separate file, locked (either digital with password or a locked cabinet), only accessible for the independent person who did the randomisation.

BLINDING: The study is double blinded. All personnel, the researchers and patients will remain blinded to the intervention being received, except the personnel performing randomisation and distributing the study medication.

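### Supplement use is an exclusion criterion, but the only form listed as covering it goes out after randomisation and no earlier check is described, so some users may be found too late

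*Combined protocol and SAP*

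**What the plan says.** - **Exclusion.** The exclusion list in section 1.2 opens with "A potential subject who meets any of the following criteria will be excluded from participation in this study" and ends with "Use of other vitamin supplements".
- **Baseline items.** Section 5.1.3 lists "use of vitamins/steroids or other supplements" among the baseline parameters, together with medication use.
- **Timing of the baseline form.** Section 5.3: "Patients will receive an automatic email invitation directly after randomisation". The Summary agrees: "At the start of taking study medication the couple is asked to fill in a questionnaire about their baseline characteristics".
- **Monthly form.** The items listed in section 5.3 are pregnancy, weight, diet, smoking, drugs and alcohol, fever, scrotal heat, tablets taken and adverse events. Supplement use is not among them.
- **Steps before randomisation.** Section 5.3 begins "Couples matching the inclusion criteria will be asked to participate in the trial", then goes to informed consent and on to randomisation. Sections 5.2 and 8.2 add no eligibility check. Section 5.2 does say that "coding starts immediately after informed consent has been obtained", so a Castor record exists before allocation.
- **Late detection.** Section 2.2 recommends a three-month wash-out for men already taking supplements. It says users are either excluded or recorded as protocol violations, and then covers the later case: "If after randomization it appears that a patient still uses other supplements (reported in the online questionnaire"). Such a man is telephoned and asked to stop, a 72-day wash-out follows, and he and his data may still be included if there is no pregnancy in that time.
- **Analysis.** Sections 5.5 and 7 specify intention to treat, with violators kept in their allocated arm. Section 7 makes supplement use without a wash-out a major deviation for the per-protocol set.

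**The concern.** An exclusion criterion works only if the information it needs is in hand before allocation. Several other exclusions in section 1.2 (endocrine, genetic, urological) are limited to known conditions, which the diagnostic work-up or the medical record can supply. Supplement use is different: someone has to ask the man. The one listed form that asks reaches him after he has been randomised, when tablets may already have started.

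Two things are at stake. First, men who take supplements in either arm narrow the contrast between Impryl and placebo, in a trial planned at only 76% power with no allowance for such men. Second, a man found late falls under the rule in section 2.2, under which his inclusion turns on whether a pregnancy occurs. Pregnancy leads to the primary outcome, so this is selection on outcome after randomisation.

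**Working it through.** **Inputs.** From section 1.3: 600 men per arm, 20% ongoing pregnancy on placebo, 26.5% on Impryl (6.5 points), two-sided alpha 5%, power 76%. The share of men using supplements at randomisation, f, is not in the documents. It is assumed equal in both arms and varied from 2% to 10%.

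**Formula.** Two proportions, pooled variance under the null, no continuity correction:

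power = Φ( [d − 1.96 × s0] / s1 ), with d = p2 − p1, s0 = √(2 × p̄ × (1 − p̄) / n), s1 = √([p1(1 − p1) + p2(1 − p2)] / n), and p̄ the mean of p1 and p2.

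**Step 1: reproduce the plan.** With p1 = 0.20, p2 = 0.265 and n = 600, s0 = 0.02439 and s1 = 0.02432. Then (0.065 − 1.96 × 0.02439) / 0.02432 = 0.707, and Φ(0.707) = 0.760. The stated 76% is reproduced.

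**Step 2: users kept in the analysis and gaining nothing.** The rate in the Impryl arm becomes p2 = 0.20 + 0.065 × (1 − f).

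| f | Men of 1200 | Difference (points) | Power |
|---|---|---|---|
| 2% | 24 | 6.37 | 74.4% |
| 5% | 60 | 6.18 | 71.9% |
| 10% | 120 | 5.85 | 67.4% |

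**Step 3: two variations.**
- If users on placebo instead reach 26.5%, so that p1 = 0.20 + 0.065 × f and p2 = 0.265, power is 74.3%, 71.5% and 66.6%.
- If users are dropped without replacement, leaving 588, 570 or 540 men per arm, power is 75.2%, 73.9% and 71.6%. Removing them therefore also costs power, though less than keeping them.

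**Step 4: set the handling rules side by side.** Section 2.2 allows exclusion of a user after randomisation and ties keeping him to the absence of pregnancy during the wash-out. Section 5.5 says violators are analysed as allocated, and section 7 says all data are analysed by intention to treat. A man found after randomisation who conceives during the wash-out is outside the inclusion rule of section 2.2 and inside the analysis under sections 5.5 and 7. Both cannot hold.

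**The case against.** A reader might infer that supplement users are always found only once they can no longer be kept out. The documents do not support that.

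- The exclusions apply to potential subjects, so formally before participation.
- Section 2.2 recommends a wash-out for existing users and speaks of a man who still uses supplements. Both suggest that the subject is raised earlier and that the questionnaire is a backstop.
- Consent follows a diagnostic work-up and counselling. The protocol prints no eligibility checklist for any criterion, so its silence here does not prove that nobody asks.
- Section 2.2 does not say which online questionnaire it means, and the forms themselves are not reproduced.

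All of this stands, and it limits the claim to some users. It does not remove it: no check before randomisation is described, and any form completed after randomisation is too late for screening, whichever one is meant.

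A reader might also extend the point to the urological, endocrine and genetic exclusions because related items appear on the baseline form. Those criteria are limited to known conditions, and neither genital operations nor steroid use is an exclusion as such. Supplement use is the one clear overlap.

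The power figures can fairly be called hypothetical. The rate of use is assumed, and zero benefit for the whole period is pessimistic because men found using supplements are asked to stop. At 2% the loss is under two points. An earlier question would rest on the same self-report and would not catch everyone.

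Finally, the conflict with intention to treat would remain for men who start supplements later, so moving the question does not cure it. It needs its own correction.

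**Conclusion.** The point holds in a limited form. The protocol describes a sequence in which the only listed question about a self-reported exclusion follows randomisation, and it plans for users to surface at that stage. Some ineligible men may therefore be randomised; how many is unknown.

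The expected harm is dilution. Power falls from 76% to about 74%, 72% or 67% if 2%, 5% or 10% of men are users. This assumes equal use in both arms, no gain from Impryl in users, and users kept in the analysis. A reader might infer bias between the arms, but under blinded 1:1 allocation users should be spread evenly, and the documents give no ground for expecting otherwise.

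The contradiction between section 2.2 and sections 5.5 and 7 does not depend on any assumed rate. Those sections must be reconciled. The change is worth making because it is cheap and the trial has little power to spare.

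**What to change.** 1. In section 5.3, add a short question at consent, when the Castor code is created, on current use of other supplements and of fertility-enhancing drugs. Require a recorded answer, checked against the exclusion criteria, before Castor allows randomisation. Staff can record it at the visit or by telephone.
2. Preferably open the baseline questionnaire at consent as well, so that answers precede the first tablet. Do not make its full completion a condition of randomisation: that would hold up slow responders and could separate consent from tablet collection for no further gain in screening.
3. Reconcile section 2.2 with sections 5.5 and 7, stating that every randomised man stays in the intention-to-treat analysis whatever his supplement use or pregnancy status. Supplement use without a wash-out can continue to define the per-protocol set, as section 7 already provides.

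The cost is one required Castor field, a few sentences of protocol text, a short extra step at consent and an occasional brief delay before randomisation.

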1.3 Sample size calculation

The overall success rate (number of ongoing pregnancies, not specified per cycle number) in IVF and ICSI in the Netherlands was respectively 19.8% and 21.5% per cycle in 2015.(23) The cumulative number of ongoing pregnancies in IUI is estimated to be around 5 to 13% per cycle, around 18% after three cycles and 20-30% after six cycles. (24-26) Based on our Radboudumc data, the ongoing pregnancy rate in EM is estimated around 20% after 6 months.

A Cochrane review ‘antioxidants for male subfertility’ estimated the increase in clinical pregnancy rates after use of antioxidants with an Odds Ratio (OR) of 3.43 (95% CI 1.92 to 6.11, $P < 0.0001$, 7 RCTs, 522 men, $I^2 = 0\%$, low quality evidence). (27) However, this concerns low quality evidence, and the included population in this Cochrane review was couples with male factor subfertility, whereas in our study we also include couples with unexplained infertility. Therefore, we assumed a more conservative OR of 1.5. Assuming a 20% ongoing pregnancy rate in the placebo group, this reflects in an expected pregnancy rate of 27.3% in the Impryl® group

The study is designed as a superiority study. Based on the above mentioned data, we expect a 7.3% increase in ongoing pregnancy number when men are treated with Impryl® compared to placebo. However, after randomization patients can directly start with both intervention and achieving a pregnancy, either spontaneously or with fertility treatment. In these first months the effect of the intervention is expected to be suboptimal due to the duration of the spermatogenesis (72 days before whole renewal). Therefore we adjusted the expected increase of 7.3% to a more realistic effect of 6.5%. We assume an equal increase in all fertility groups (meaning EM, IUI and IVF/ICSI) from 20% to 26.5%.

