The ratio between the 3 fertility treatment groups (EM 1: IUI 3: IVF/ICSI 2) is based on the number of new patients treated at Radboudumc and the sites each year. To test the effect of Impryl on the probability of ongoing pregnancy, a sample size of 600 men per treatment group (1200 in total) is needed, assuming differences in ongoing pregnancy rates of 6.5% and an expected ongoing pregnancy rate of 20% in the placebo group, with a two-sided alpha of 5% and a beta of 24% (i.e. 76% power). As we expect the number of participants lost to follow up to be minimal. We will allocate 600 patients in both intervention and control arm. Figure 1 shows the distribution of the number of participants for the 3 different types of fertility treatment (EM, IUI and IVF/ICSI).

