6.2 AEs, SAEs and SUSARs

6.2.1 Adverse events (AEs)

Adverse events are defined as any undesirable experience occurring to a subject during the study, whether or not considered related to Impryl®. All adverse events reported by the subject or observed by the investigator or his staff will be recorded.

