6.4 Follow-up of adverse events

There will be no follow-up of adverse events. There are no adverse events reported in previous use of Impryl. Therefore these are not expected. However, all SAEs and SUSARs will be followed until they have abated, or until a stable situation has been reached. Depending on the event, follow up may require additional tests or medical procedures as indicated, and/or referral to the general physician or a medical specialist. SAEs need to be reported till end of study within the Netherlands, as defined in the protocol

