9.5 Temporary halt and (prematurely) end of study report

The sponsor will notify the accredited METC and the competent authority of the end of the study within a period of 90 days. The end of the study is defined as the last patient's last visit, in case of not achieving a pregnancy this will be a telephonic consultation.

The sponsor will notify the METC immediately of a temporary halt of the study, including the reason of such an action.

In case the study is ended prematurely, the sponsor will notify the accredited METC and the competent authority within 15 days, including the reasons for the premature termination.

Within one year after the end of the study, the investigator/sponsor will submit a final study report with the results of the study, including any publications/abstracts of the study, to the accredited METC and the Competent Authority.

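### SAEs, including congenital anomalies, must be reported until end of study, but no scheduled contact asks about them once the monthly forms end at month 6 or at pregnancy

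*Combined protocol and SAP*

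**What the plan says.** **The duty.** Section 6.2.1 sets a wide window: "Adverse events are defined as any undesirable experience occurring to a subject during the study". Section 6.4 says that ordinary AEs will not be followed up, but keeps SAEs and SUSARs apart and states: "SAEs need to be reported till end of study within the Netherlands, as defined in the protocol". The SAE definition in 6.2.2 includes congenital anomalies. Adverse effects are a secondary endpoint (5.1.2), to be summarised (section 7).

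**The means.** Under Lifestyle and outcome characteristics, 5.3 puts one adverse-event question in the monthly online form. The Summary gives six such forms. Section 5.3 then says: "When a pregnancy has been reached during the 6 months use of study medication the monthly questionnaires will be stopped". Its reason is that lifestyle and compliance data are no longer needed; safety is not mentioned. Study product also stops at a positive pregnancy test, or at month 6.

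**The last contact.** The month-15 questionnaire in 5.3 lists fertility treatment, pregnancy, miscarriage and childbirth, with delivery details including complications, birth weight and sex. It lists no general AE or SAE item and no anomaly item. Non-responders get a reminder e-mail and then a telephone call, to the man or his general practitioner. Section 9.5 ties end of study to the last visit and adds: "in case of not achieving a pregnancy this will be a telephonic consultation". Section 5.3 schedules no such call for couples without a pregnancy.

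**The concern.** A reporting window that runs to end of study should have some contact behind it that asks the question. Here the last active question comes at month 6 at the latest, and earlier in couples who conceive.

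After that an SAE reaches the sponsor only if the man volunteers it or staff happen to learn of it. The design makes this less likely: it aims for no extra site visits, and the outcome ultrasound may be done in a midwife practice. Couples still in fertility treatment probably see trial staff more often than couples who have conceived, so passive reporting may also differ by pregnancy status.

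Congenital anomaly is the clearest case. The protocol calls it an SAE, it will usually become known long after the monthly forms have stopped, and the one later form does not list it. There is no DSMB (6.5) and no interim analysis (7.1), so no other safety review would bring such events to light.

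**Working it through.** **Passages side by side**

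| Question | Where | Answer |
|---|---|---|
| How long are SAEs reportable? | 6.4 | To end of study |
| Is congenital anomaly an SAE? | 6.2.2 | Yes |
| Which scheduled form asks about AEs? | 5.3 | Monthly form only |
| When does it end? | Summary; 5.3 | After six forms, or at pregnancy |
| Does the month-15 form list AEs, SAEs or anomalies? | 5.3 | No |
| Is the closing call in 9.5 scheduled? | 5.3 | No; calls go to non-responders only |
| Is there another route? | 6.2.1; 6.2.2 | Yes, passive: reported or observed AEs are recorded, and SAEs known to the investigator are reported |

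**Inputs for the size**

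- Follow-up per couple: 15 months (Summary, 5.1.2, 5.3).
- Active questioning: at most 6 months (Summary).
- Rates: "We assume an equal increase in all fertility groups (meaning EM, IUI and IVF/ICSI) from 20% to 26.5" per cent (1.3).
- Arms: 600 each, 1:1 (1.3, 5.2).
- Assumed, because the documents do not give it: t, the mean month at which questioning stops in couples who conceive. Base case t = 3, range 1 to 5.

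**The plan's own figure.** The plan gives no figure for questioned time. Its sample-size figures, the source of the rates, do reproduce. With p̄ = (0.20 + 0.265)/2 = 0.2325:

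z = [0.065 × √600 − 1.96 × √(2 × 0.2325 × 0.7675)] / √(0.20 × 0.80 + 0.265 × 0.735) ≈ (1.592 − 1.171)/0.596 ≈ 0.71

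This is a power of 76.0%, as stated.

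**Floor, with no timing assumption.** A couple without a pregnancy has (15 − 6)/15 = 60% of follow-up without an active question. No couple has less.

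**With conceptions.** Mean questioned months in an arm with pregnancy rate p are (1 − p) × 6 + p × t. At t = 3:

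- Placebo: 0.80 × 6 + 0.20 × 3 = 5.40 months; share not asked 1 − 5.40/15 = 64.0%.
- Impryl: 0.735 × 6 + 0.265 × 3 = 5.205 months; share not asked 1 − 5.205/15 = 65.3%.
- Overall: 1 − [(5.40 + 5.205)/2]/15 = 64.7%.

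| t (months) | Placebo (months) | Impryl (months) | Overall not asked | Difference between arms |
|---|---|---|---|---|
| 1 | 5.00 | 4.675 | 67.8% | 0.325 month (6.5%) |
| 3 | 5.40 | 5.205 | 64.7% | 0.195 month (3.6%) |
| 5 | 5.80 | 5.735 | 61.6% | 0.065 month (1.1%) |

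**Trigger.** The forms stop at any pregnancy, while the rates above are for ongoing pregnancy. If ongoing pregnancies are 70% to 80% of all pregnancies (assumed), the overall share at t = 3 is 66.6% to 65.8%. The picture does not change.

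**The case against.** The best defence is that the AE question follows exposure. Product and monthly forms stop at the same point, and the form on which a pregnancy is reported also carries an AE question. The events listed in the objectives (gastro-intestinal complaints, headache, rash and the like) are mainly short-term tolerability effects, for which asking during use is reasonable. Section 6.4 can also be read as a duty to report what becomes known, not a promise to ask, and passive SAE reporting after treatment is a defensible choice for a food supplement. Most of this stands. It does not explain why a form sent to every couple at month 15 leaves out events that the protocol itself calls SAEs.

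A reader might infer three stronger things that the documents do not support:

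- **That some 65% of follow-up is uncollected.** It is not actively asked about. Sections 6.2.1 and 6.2.2 keep the passive route open with no month-6 limit, and the month-15 form asks about miscarriage and delivery complications.
- **That the arm with more pregnancies will look materially safer.** The expected difference in questioned time is about 0.2 month, and less product use in that arm would genuinely mean fewer on-treatment events. At an assumed 10% AE risk, 3.6% less questioned time gives about 10% × 0.964 = 9.6%. The standard error of the difference between arms is √(2 × 0.10 × 0.90/600) = 1.7 percentage points.
- **That collection depends on the primary outcome.** The trigger is any pregnancy, a precursor of the ongoing pregnancy confirmed by ultrasound at 10-12 weeks.

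**Conclusion.** The point holds as a gap between the stated SAE window and the scheduled means of filling it. At least 60% of each couple's 15 months has no active AE or SAE question. That figure rests only on the six monthly forms and the 15-month follow-up. The figure of about 65% (range about 62% to 68%) also needs the planned pregnancy rates and an assumed mean stop at month 3 (range 1 to 5).

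What is exposed is the capture of SAEs after product stop, above all congenital anomalies. On-treatment AEs are largely covered, and the expected imbalance between arms is too small to count as a material bias. The primary analysis is not affected. This is an inexpensive improvement that should be made, together with a reconciliation of 5.3, 6.4 and 9.5.

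**What to change.** 1. **Section 5.3, month-15 questionnaire and its telephone fallback, all couples.** Add one item on any hospital admission or serious illness of the man since his last monthly form, and one on any congenital anomaly in the child. Where the child is not yet born when the form is completed, record that, so that a blank is not read as no anomaly.
2. **Section 9.5.** Define each couple's last contact as completion of that questionnaire or call. This gives the SAE window in 6.4 a definite end and removes the unscheduled telephone consultation.
3. **Section 5.3, monthly forms.** State that the form reporting a pregnancy also carries the AE question, so that product use is covered to its end.
4. **Section 7.** Report on-treatment AEs also per man-month on product. Use time on product as the denominator, so that events and time end at the same point. The date of the positive test and the reported tablet use, both already collected, supply most of what is needed.

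Monthly AE e-mails after conception are not needed, since those men are off product. The cost is one or two extra questions on an existing form, a sentence in 9.5 and one column in a table.
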